Capsules will be administered orally BID. Study staff will administer the first dose of ALKS 8700 at Visit 2 (Day 1). From that point on during the treatment period, the staff will dispense ALKS 8700 for participants' self-administration. Subjects will be instructed to take study treatment with or without food. However, subjects will be instructed to avoid taking study treatment with a high-fat, high-calorie meal.

Sample Size Determination:

No formal sample size calculation is performed for this study. A sample size of approximately 1000 subjects will contribute to the

CONFIDENTIAL

The information contained herein may not be used, disclosed, or published without the written consent of Biogen MA Inc.

long-term safety experience of ALKS 8700 in subjects with RRMS, taking into account International Council for Harmonisation guidance on the extent of patient exposures required to assess clinical safety for a new drug.

Visit Schedule: Subjects will have up to 16 visits during the study.

Study assessments conducted at each visit are listed in the Schedule of Activities ([Table 1](#)).

Duration of Study  
Participation: Study duration for each subject will be approximately 102 weeks:

- 4-week screening period (De Novo Subjects only)
- 96-week treatment period
- 2-week follow-up period

[figure not shown]
Benefit-Risk Analysis: The potential risks related to participation in this study are justified by the anticipated benefit to subjects.  
  
The modified-release oral dosage form may provide an MMF exposure profile that may limit GI effects associated with DMF treatment while maintaining efficacy. Accordingly, ALKS 8700 has the potential to address an unmet medical need for patients with relapsing forms of MS who are unable to tolerate DMF.

CONFIDENTIAL

The information contained herein may not be used, disclosed, or published without the written consent of Biogen MA Inc.

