### 9.1. Clinical Efficacy Assessments

ALKS 8700 treatment effect over time will be assessed in an exploratory manner based on the following:

- [REDACTED]

- Clinical assessments
  - MS relapse
  - T25-FW
  - Progression of disability as assessed by EDSS
- Other assessments
  - EQ-5D-5L
  - SF-12

[REDACTED]

CONFIDENTIAL

The information contained herein may not be used, disclosed, or published without the written consent of  
Biogen MA Inc.

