The T25-FW score and change from baseline during the Treatment Period will be summarized by enrollment group and overall.

No Evidence of Disease Activity (NEDA)

Both NEDA-3 and NEDA-4 definitions will be used to identify subjects with NEDA. The definition of NEDA-3 encompasses a combination of three related measures of disease activity: no relapses, no confirmed disability progression sustained for 12 weeks as measured on EDSS and no MRI disease activity, defined as no new GdE lesions and no new or enlarging T2 hyperintense lesions. The definition of NEDA-4 is the above definition of NEDA-3 with the addition of a mean annualized rate of brain volume loss (AR-BVL) of less than 0.4% where AR-BVL is derived from percentage brain volume change from baseline (PBVC) and is calculated as $((\text{PBVC}/100+1)^{(365.25/\text{days})}-1)*100$ [2].

Proportion of Subjects with NEDA-3 and NEDA-4 at Week 96 will be summarized by enrollment group and overall. Estimated proportion of subjects with NEDA-3 and NEDA-4 at week 96 will be estimated using Kaplan-Meier product-limit method and reported by enrollment group and overall.

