8. PROGRAMMING SPECIFICATIONS

Programming specifications will be provided in a separate document.

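### The NEDA-4 brain volume formula returns signed change, not loss, so as written every subject with net brain volume loss meets the 'less than 0.4%' criterion

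*SAP*

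**What the plan says.** SAP section 3.5.3 (No Evidence of Disease Activity) defines NEDA-4 as NEDA-3 plus "a mean annualized rate of brain volume loss (AR-BVL) of less than 0.4% where AR-BVL is derived from percentage brain volume change from baseline" (PBVC). It then gives the calculation:

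AR-BVL = ((PBVC/100 + 1)^(365.25/days) − 1) × 100

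The formula has no leading minus sign and no absolute value, and the readable text gives no other sign convention for PBVC.

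The result feeds a reported output: "Proportion of Subjects with NEDA-3 and NEDA-4 at Week 96 will be summarized by enrollment group and overall". The same paragraph adds a Kaplan-Meier estimate at Week 96.

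Two statements limit what can be concluded. SAP section 8 says "Programming specifications will be provided in a separate document", and protocol section 9.1 says that "ALKS 8700 treatment effect over time will be assessed in an exploratory manner".

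**The concern.** The threshold and the formula run in opposite directions. The threshold is on a loss scale, where a larger positive number is worse and a subject qualifies by staying below 0.4. The formula is on a change scale, where loss is negative. Applying the upper limit of 0.4 to the formula's output lets every loss through and penalizes only gains.

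The fourth NEDA component exists to exclude subjects with atrophy. Under literal coding it excludes none of them. Apart from the few removed for volume gain, NEDA-4 would then be the same as NEDA-3 while being presented as a stricter measure, and the proportion would be too favourable whenever the average change is a loss. Independent double programming from this text would not reveal the error, because both programmers would implement the same printed rule.

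**Working it through.** The plan gives no worked AR-BVL value and no expected NEDA-4 proportion, so there is no figure to reproduce. The formula was evaluated directly.

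**Inputs**
- Formula and 0.4% threshold: SAP section 3.5.3.
- PBVC: a change from baseline, so negative for loss on the ordinary reading.
- Days: 672, from Day 1 to the Week 96 visit on Day 673 ("96-week treatment period"; 96 × 7 = 672). The visit window is ±5 days, giving 667 to 677.

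**Step 1: algebra.** If PBVC < 0, then PBVC/100 + 1 < 1. Any positive power of a number between 0 and 1 is below 1, so the result is negative and therefore below 0.4. This holds for any loss and any number of days. A grid of 200,000 negative PBVC values at 29, 337, 672 and 1000 days gave no exception.

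**Step 2: worked values at 672 days** (365.25/672 = 0.5435)

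| PBVC | Formula result | As printed (result < 0.4) | As worded (loss < 0.4) |
|---|---|---|---|
| −4% | −2.194 | meets | fails |
| −2% | −1.092 | meets | fails |
| −1% | −0.545 | meets | fails |
| −0.5% | −0.272 | meets | meets |
| +1% | +0.542 | fails | meets |

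**Step 3: cut-offs on the PBVC scale.** Inverting the formula:
- As worded: PBVC = (0.996^(672/365.25) − 1) × 100 = −0.735%. Subjects above this value meet the criterion. Over 667 to 677 days the cut-off runs from −0.729% to −0.740%.
- As printed: PBVC = (1.004^(672/365.25) − 1) × 100 = +0.737%. Subjects at or above this value fail, and everyone else meets the criterion.

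**Step 4: possible size.** The documents give no distribution of brain volume change, so this step rests on assumptions. Let X be the annualized change in % per year, taken as normal.

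| Mean | SD | As printed, P(X < 0.4) | As worded, P(X > −0.4) |
|---|---|---|---|
| 0 | 0.4 | 0.841 | 0.841 |
| 0 | 0.6 | 0.748 | 0.748 |
| −0.2 | 0.4 | 0.933 | 0.691 |
| −0.2 | 0.6 | 0.841 | 0.631 |
| −0.4 | 0.4 | 0.977 | 0.500 |
| −0.4 | 0.6 | 0.909 | 0.500 |
| −0.6 | 0.4 | 0.994 | 0.309 |
| −0.6 | 0.6 | 0.952 | 0.369 |

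For means from −0.2 to −0.6, 84–99% meet the component as printed, against 31–69% as worded.

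The change in NEDA-4 cannot exceed the NEDA-3 proportion. If NEDA-3 is 30% to 70% and independent of brain volume, the difference is NEDA-3 × the component difference (taken before rounding):
- Smallest: 0.30 × 0.211 = 0.063 (mean −0.2, SD 0.6).
- Largest: 0.70 × 0.685 = 0.480 (mean −0.6, SD 0.4).
- Intermediate example (mean −0.4, SD 0.6, NEDA-3 50%): 0.454 as printed against 0.250 as worded.

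**The case against.** The strongest reply is that the intent is plain. The sentence says loss, and a programmer who reads it would reverse the sign. The text around it is also incomplete: SAP numbering passes from 3.5.1 to 3.5.3 across blacked-out material, and dataset and programming specifications are separate documents. Any of these could define the sign of PBVC. If PBVC were entered as a positive loss, the printed rule would work almost as intended, with a cut-off of 0.737% instead of 0.735% at 672 days.

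This limits what can be said about the results: nothing shows that the program is wrong. It does not rescue the SAP text. The NEDA paragraph is readable, calls PBVC a change from baseline, and gives a complete formula and cut-off that do not fit together. A specification that added the minus sign would be departing from the SAP formula.

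Two further objections concern the numbers. First, protocol section 12.3 sets the Rollover baseline at the baseline visit of the antecedent study, and SAP section 3.5.1 allows antecedent-study assessments to be carried over as baseline. The interval can therefore differ from 672 days. That is fair: the PBVC cut-offs illustrate a Day 1 baseline, and a different interval moves them without touching the sign error. Second, the 6 to 48 point range rests on assumed means, SDs, NEDA-3 proportions and independence. That also stands. Admitting a mean change of zero takes the lower end to 0, and if subjects who meet NEDA-3 lose less volume than others, the upper end is too high.

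Finally, only one component of one of the two NEDA definitions is involved, in an exploratory, descriptive analysis. That bears on priority, not on whether the text is right.

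**Conclusion.** The concern holds. The printed formula and threshold contradict the worded criterion, and followed literally they exclude nobody for atrophy. This is certain from the algebra, provided PBVC is a signed change that is negative for loss, as its name says.

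Whether reported results would be affected depends on the program, which cannot be seen. If it follows the SAP literally, the NEDA-4 proportion is overstated when the average change is a loss. The size cannot be derived from the documents, and the 6 to 48 percentage points hold only under the stated assumptions. NEDA-3, relapse, EDSS and all safety outputs are untouched, and no test or error rate is involved. The correction should be made, but the trial's main conclusions do not depend on it.

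**What to change.** Keep the worded criterion and correct the formula in SAP section 3.5.3:

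AR-BVL = −((PBVC/100 + 1)^(365.25/days) − 1) × 100, where a negative PBVC denotes loss; the criterion is met if AR-BVL < 0.4%.

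This is equivalent to requiring an annualized PBVC greater than −0.4% per year. Confirm that the programming specification and the program use this sign, and that PBVC is stored as negative for loss. If it is stored as a positive loss, the added minus sign would itself reverse the rule.

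Do not use the absolute value. It would fail subjects whose volume rises by 0.4% per year or more: at an assumed mean of −0.2 and SD of 0.6, the component pass rate would be 0.472 instead of 0.631.

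The cost is one minus sign, a short statement of the convention and a program check. The planned proportion and Kaplan-Meier summaries need no change on this account. If the program now follows the printed formula, the reported NEDA-4 proportion will become less favourable when the average change is a loss.

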3.5.4. Patient Reported Outcomes

The following patient reported outcomes will be summarized for each enrollment group and overall:

- The change from baseline in the Short Form 12 Health Survey (SF-12) component and summary scores through Week 96
- The changes from baseline in the EQ-5D-5L visual analog scale (VAS) scores through Week 96

Short Form 12 Health Survey (SF-12) Component Scores

Quality of life will be assessed using the 12-item Short-Form health survey Version 2 (SF 12v2) [3]. The 12-item Short Form or SF-12 is a generic quality of life (QOL) measure based on the SF-36 Health Survey. The SF-12 captures approximately 90% of the variance of the SF 36. The SF-12 provides two summary indices of health-related quality of life: the Physical Component Summary (SF-12 PCS) and the Mental Component Summary (SF-12 MCS). SF-12 PCS and SF12 MCS scores will be computed using the transformed scores of 12 questions and range from 0 to 100 (Mean=50, standard deviation [SD] =10 in the general US population), where zero indicates the lowest level of health measured by the scales and 100 indicates the highest level of health [3].

EQ-5D-5L Visual Analog Scale (VAS) Scores

The 5-level EQ-5D version (EQ-5D-5L) [4] is designed for self-completion by subjects and consists of 2 pages - the EQ-5D-5L descriptive system and the EQ visual analog scale (VAS). The EQ-5D-5L descriptive system comprises the following 5 dimensions: mobility, self-care, usual activities, pain/discomfort, and anxiety/depression. Each dimension has 5 levels: no problems, slight problems, moderate problems, severe problems, and extreme problems. The EQ VAS records the respondent's self-rated health on a vertical, visual analog scale where the anchors are labeled 'Best imaginable health state' (score of 100) and 'Worst imaginable health state' (score of 0). The EQ-5D-5L descriptive system can be converted into a single summary EQ-5D Index [5].

The Patient Reported Outcomes scores and changes from baseline during the Treatment Period will be summarized by enrollment group and overall.

3.6. Safety Analyses

3.6.1. General Considerations

All safety analyses will be carried out using the safety analysis set ([Section 3.1.1.1](#)) and will be summarized by enrollment group and overall unless specified otherwise.

3.6.2. Adverse Events

All adverse events (AEs) will be coded by System Organ Class and Preferred Term using the Medical Dictionary for Regulatory Activities MedDRA version 20.1 or higher. The verbatim term will be included in the AE listings.

AEs will be identified as emerging in the treatment period and the follow up period. During the treatment period, an AE will be considered as treatment-emergent AE (TEAE) if the event starts or worsens on or after the date of first dose of study drug in the current study. The Treatment Period is defined as the first dose start date to the date of end of treatment (EOT) in the current study, inclusive.

During the follow up period, post-discontinuation emergent AEs (PDEAEs), defined as AEs that started or worsened after date of the EOT visit, will be summarized. For PDEAEs, the greatest severity before or on the date of the EOT visit will be used as the benchmark for the comparison

of the AEs occurring during the follow up period. The Follow-up Period is defined as the period between the date of the EOT visit plus 1 day and the last study visit, inclusive.

An overview table, including number of subjects with TEAEs, serious AEs (SAEs), AEs leading to study discontinuation, study drug-related TEAEs, and PDEAEs will be provided. Adverse events leading to study discontinuation and SAEs leading to death will be summarized in the period when the discontinuation or death occurred.

The following summary tables will be provided for the treatment period by enrollment group and overall:

- TEAEs by System Organ Class and Preferred Term
- TEAEs by System Organ Class, Preferred Term, and severity
- TEAEs by System Organ Class, Preferred Term, and relationship
- Study drug related TEAEs by System Organ Class and Preferred Term
- TEAEs experienced by $\geq 5\%$ of subjects by System Organ Class and Preferred Term
- SAEs by System Organ Class and Preferred Term
- AEs leading to study discontinuation by System Organ Class and Preferred Term
- Adverse Events of Special Interest by System Organ Class and Preferred Term

In addition, an AE overview table and AEs by System Organ Class and Preferred Term for PDEAEs during the Follow-up Period will be provided.

All AE tables will be sorted by System Organ Class and then Preferred Term in decreasing frequency based on all subjects in the Safety Population.

A subject having the same AE (as determined by the coded MedDRA preferred term) more than once will be counted only once in the number and percentage of subjects calculation for that AE. Similarly, if a subject has more than one AE in a SOC, the subject will be counted only once in the total number and percentage of subjects with an AE for that SOC. If a subject has the same AE on multiple occasions, the highest severity (severe > moderate > mild) recorded for the event will be presented in the AE by severity summary. Similarly, if a subject has the same AE on multiple occasions, the closest relationship to study drug (related > not related, where related includes definitely related, probably related, and possibly related; and not related includes probably not related and definitely not related) recorded for the event will be presented in the AE by relationship summary.

Renal impact defined by baseline GFR subgroup will be summarized for TEAE and SAE by System Organ Class and Preferred Term.

Age subgroup (age < 55 and age ≥ 55 at baseline) will be summarized for TEAE and SAE by System Organ Class and Preferred Term.

All AEs will be included in the listings. Supporting listings of SAEs, AEs leading to study discontinuation, and AEs leading to death will be provided. Subjects with PDEAEs in the Follow-up Period will also be listed.

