During the 96-week treatment period (Visits 2-15), subjects will return to the clinic for periodic scheduled visits for the assessment of safety, tolerability, PK (in a subset of de novo subjects in selected sites), and clinical status. Two safety and tolerability assessments by phone will be scheduled (one between Visits 2 and 3 and one between Visits 3 and 4). See [Figure 1](#) for a study schematic.

Subjects will return to the clinic for a safety follow-up visit (Visit 16) 2 weeks after the end of treatment visit (Visit 15). Any subject who prematurely discontinues from either study treatment or the study will be asked to return to the clinic for an early termination (ET) visit (Visit 15) as well as a safety follow-up visit 2 weeks later (Visit 16).

Subjects who complete the study or who terminate the study early and have a last measured lymphocyte count  $< 0.8 \times 10^3/\mu\text{L}$  will return to the clinic for additional lymphocyte count monitoring visits every 2 months starting from Visit 16 for a period of 6 months (i.e., a maximum of 3 visits) or until lymphocyte counts reach normal limits ( $\geq 0.91 \times 10^3/\mu\text{L}$ ), whichever occurs first.

A treatment completer will be a subject who completes the 96-week treatment period (i.e., through Visit 15). Subjects completing the follow-up visit will be categorized as completing the study.

The end of study date for a subject may be the last study visit, last follow-up telephone conversation, or last protocol-specified assessment, or if the subject has ongoing AEs that are being followed, the date may be the date of AE resolution.

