## **12.6. Methods of Analysis for Safety Endpoints**

The safety analysis will be carried out using the safety population. Reported AE terms will be coded using the Medical Dictionary for Regulatory Activities.

Safety assessments will be summarized using descriptive statistics along with supportive listings. The number and percentage of TEAEs will be summarized by system organ class, and preferred terms within each system organ class. SAEs and AEs resulting in treatment discontinuation will be summarized.

Observed values and change from baseline in laboratory parameters, vital signs, ECG parameters, and scores on the C-SSRS will be summarized by study visit. The number and percentage of subjects who have met potentially clinically significant criteria at any postbaseline visit will be summarized.

Listings will be provided for all safety endpoints.

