3.6.3. Deaths, Serious and Other Significant Adverse Events

The number and percentage of subjects with at least one SAE (regardless treatment emergent or not) will be summarized by System Organ Class and Preferred Term for the Safety Population. Deaths and AEs leading to discontinuation (regardless treatment emergent or not) will be summarized similarly.

Supporting listings of serious AEs and AEs leading to study discontinuations will be provided. Subjects who died during the study will also be listed.

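### SAP 3.6.2 reports AEs that led to study discontinuation where Protocol 12.6 plans AEs that led to treatment discontinuation, and SAP Section 5 does not declare the change (minor)

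*SAP*

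**What the plan says.** Protocol 12.6 names only a few AE summaries. One of them is: "SAEs and AEs resulting in treatment discontinuation will be summarized".

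SAP 3.6.2 uses the other event, discontinuation of the study, in its overview table, in its treatment-period table by System Organ Class and Preferred Term, and in its listing: "Supporting listings of SAEs, AEs leading to study discontinuation, and AEs leading to death will be provided". It places these AEs by when the subject discontinued: "Adverse events leading to study discontinuation and SAEs leading to death will be summarized in the period when the discontinuation or death occurred".

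SAP 3.6.3 adds a summary that does not say which discontinuation is meant: "Deaths and AEs leading to discontinuation (regardless treatment emergent or not) will be summarized similarly". The listing that goes with it is again for study discontinuations.

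SAP Section 5, which is the place for departures from the protocol, mentions only the COVID-19 assessments.

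**The concern.** The first study objective is long-term safety and tolerability, and the rationale for the drug is better gastrointestinal tolerability than DMF. Protocol 3.3 notes that GI events were the leading cause of AE discontinuations with DMF. How many subjects stopped taking the drug because of an AE is therefore a key descriptive result, and it is the one that Protocol 12.6 plans.

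The SAP's main AE section counts a different event without saying that this is a change. If the two events are recorded separately, a subject who stops the drug for an AE but is not recorded as having left the study would be absent from the table that readers will use for tolerability.

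**Working it through.** The plan gives no figure to reproduce. Protocol 12.8 states that there is no formal sample size calculation, and neither document gives a discontinuation rate. The check is therefore a comparison of the text.

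1. **Which event each output names.**
   - Protocol 12.6, planned summary: treatment.
   - SAP 3.6.2, overview table: study.
   - SAP 3.6.2, table by System Organ Class and Preferred Term: study.
   - SAP 3.6.2, listing: study.
   - SAP 3.6.3, summary: not specified.
   - SAP 3.6.3, listing: study.

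   Of the five SAP outputs, four name the study, one is unqualified, and none names treatment.

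2. **Whether the documents treat these as two events.** Protocol 5.2 provides for both: "Any subject who prematurely discontinues from either study treatment or the study will be asked to return to the clinic". Protocol 8.1 covers stopping treatment and requires its primary reason on the eCRF. Protocol 8.3 covers leaving the study and requires its own reason on the eCRF. SAP 3.8 also names both kinds when it describes COVID-19 data. The distinction is available in the data, and the SAP uses it elsewhere.

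3. **One subject followed through the rules.** A subject stops the drug for an AE. Under Protocol 8.1 the subject is asked to attend the ET visit (Visit 15) and then Visit 16 two weeks later. Protocol 5.2 and 8.3 categorize anyone who completes the follow-up visit as completing the study. Taken literally, this subject has a treatment discontinuation but no study discontinuation. The AE belongs in the summary planned in Protocol 12.6 but could be missing from the SAP 3.6.2 table and listing.

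4. **What is not lost.** The AE itself still appears in the TEAE tables and in the listing of all AEs. Only its count as a reason for discontinuation is at risk.

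5. **Scale.** With about 1000 subjects (Protocol 12.8), one omitted subject changes the overall rate by 1/1000 = 0.1 percentage point. The number of such subjects cannot be derived from the documents. Enrollment-group sizes are not given, so the change within a group cannot be computed either.

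**The case against.** The best defence is that this is loose wording rather than a changed analysis. Several passages support it.

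- SAP 1.2 describes the ET-and-Visit-16 pathway for subjects who prematurely leave the study, where Protocol 5.2 and 8.1 name both treatment and study. Protocol 5.5 also names only the study. The SAP may therefore use the phrase for any early stop.
- SAP 3.1.2 describes study completion as covering both the treatment and the follow-up periods. On that definition, an early drug-stopper is not a completer even after attending Visit 16.
- The design has no scheduled off-drug continuation beyond the ET visit, Visit 16 and, where needed, lymphocyte monitoring. The two events will often coincide.
- The protocol itself mixes the terms. The lymphocyte rule in 7.2 moves from stopping treatment to leaving the study, and pregnancy is a treatment discontinuation in 8.1 but a study withdrawal in 11.3.1.
- The unqualified summary in SAP 3.6.3 may already be the one the protocol planned. SAP 3.3 ties the word post-discontinuation to the last dose of study drug, which favours that reading.
- Dataset specifications, programming specifications and mock tables are separate documents (SAP Sections 6, 8 and 9) and may settle the matter.

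Most of this stands as a limit on the size of the effect. It does not remove the mismatch. Reading 3.6.3 as the planned summary is an inference, and its own listing names the study. The literal completer sentence in Protocol 5.2 and 8.3 points the other way from SAP 3.1.2. The SAP text does not commit to the protocol's summary, and Section 5 is silent.

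**Conclusion.** The mismatch is real and undeclared, and it concerns a tolerability summary that Protocol 12.6 names. Its numerical effect is unknown and may be small or nil. Any omission rests on two assumptions: that the literal completer sentence governs how these subjects are recorded, and that 3.6.3 does not deliver the planned summary. Because the analyses are descriptive, a reported rate could be affected but no test could be. The severity is minor.

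Three stronger readings are tempting and are not supported.

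- A reader might infer that the protocol's summary has been dropped. SAP 3.6.3 may still supply it, so this cannot be said.
- A reader might infer that these AEs move into the Follow-up Period or fall outside both periods. The argument would start from Protocol 5.2, where "The end of study date for a subject may be the last study visit, last follow-up telephone conversation, or last protocol-specified assessment" and, further, "if the subject has ongoing AEs that are being followed, the date may be the date of AE resolution". It would then set that date against the SAP's Follow-up Period, "the period between the date of the EOT visit plus 1 day and the last study visit, inclusive". However, no passage makes the end of study date the discontinuation date, and SAP 3.1.2 counts subjects who left the study during the treatment period, which implies that an earlier date can be used.
- A reader might infer a material understatement of the discontinuation rate. No counts are given on which to base one.

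**What to change.** In SAP 3.6.2 and 3.6.3, replace study discontinuation with discontinuation of study treatment in the overview, the table and the listings, and add the same qualifier to the 3.6.3 summary. Identify these AEs from the treatment-stop reason on the eCRF (Protocol 8.1) and the action taken for each AE (Protocol 11.3.1). Assign them to a period by treatment-stop date. If a summary of AEs that led to study discontinuation is also wanted, keep it under its own label. If the sponsor does intend to depart from Protocol 12.6, declare it in SAP Section 5.

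The cost is a few words in the SAP and, if both summaries are kept, one extra row or table. No new data are needed. The reported rate may stay the same or become slightly less favourable.

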#### 6.1.1. Rollover Subjects

In order to qualify for participation in this study, Rollover Subjects must meet all of the following criteria:

1. Is willing and able to provide informed consent.
2. Capable of understanding and complying with the protocol.
3. Agrees to use an acceptable method of contraception for the duration of the study and for 30 days after any study treatment administration or is surgically sterile or postmenopausal (see [Section 11.5](#)).
4. Completed the full treatment period of any eligible study of ALKS 8700 within 7 days of Visit 2.

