3. DATA ANALYSES

3.1. Study Population

The study population, defined as all enrolled subjects who receive at least one dose of ALKS 8700, will be divided into three enrollment groups for summarizing safety and efficacy data:

1. De Novo Subjects
2. Rollover Subjects who were in ALKS8700 treatment group
3. Rollover Subjects who were in DMF treatment group

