3.4. Treatment Adherence Rate and Extent of Exposure

Treatment adherence will be defined as: (number of capsules taken) / (number of capsules expected to be taken) * 100. When a subject discontinues treatment early, the number of capsules that should have been taken is based upon the duration the subject was on treatment.

Total number of days the subject is on study drug will also be summarized as a continuous variable and categorized into 12-week intervals. Days on study drug will be calculated as the number of days from date of first dose to date of last dose plus 1.

[figure not shown]
Treatment adherence and exposure will be summarized by enrollment group and overall. Supportive listings will be provided.

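### Adverse event incidence is planned only as crude percentages of subjects dosed, which understates 96-week risk for events that accumulate over time

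*SAP*

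**What the plan says.** The safety objective in Protocol section 4 covers up to 96 weeks of treatment. For AEs, Protocol 12.6 states: "The number and percentage of TEAEs will be summarized by system organ class". SAP 3.6.2 lists the tables, beginning with "TEAEs by System Organ Class and Preferred Term", and gives the counting rule: a subject with repeated events under one preferred term "will be counted only once in the number and percentage of subjects calculation for that AE". SAP 3.6.3 and 3.6.4 treat serious and special-interest AEs in the same way, by system organ class and preferred term. All these analyses use the safety population.

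On columns, SAP 3.6.2 says: "The following summary tables will be provided for the treatment period by enrollment group and overall". The groups in SAP 3.1 are De Novo subjects, rollovers from ALKS 8700, and "Rollover Subjects who were in DMF treatment group". A rollover must have met this criterion in Protocol 6.1.1: "Completed the full treatment period of any eligible study of ALKS 8700 within 7 days of Visit 2". Treatment-emergent events count from the first dose in the current study.

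Exposure is derived in SAP 3.4: "Days on study drug will be calculated as the number of days from date of first dose to date of last dose plus 1". It is summarized by enrollment group, as a continuous variable and in 12-week bands, but no AE analysis uses it. In SAP 3.5.3 the relapse rate is divided by patient-years, and relapse, confirmed progression and NEDA proportions are estimated by Kaplan-Meier.

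**The concern.** A subject who stops at week 4 and one who completes week 96 carry the same weight in the denominator of a crude percentage, but the early leaver had far less time in which to have an event. For an outcome whose risk continues throughout treatment, the percentage therefore understates the 96-week risk, and the gap widens with dropout.

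Some unequal follow-up is to be expected. Subjects who withdraw after the first dose may not be replaced (Protocol 8.3). Protocol 5.3 and 7.2 describe discontinuation for continuing intolerance by Visit 4 and for persistent laboratory abnormalities. Rollovers had already completed a treatment period and De Novo subjects had not, so attrition could plausibly differ between the columns, although the documents do not show that it will.

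The categories most exposed are those for which long-term data are wanted: infections, malignancies, lymphopenia, and liver and renal injury. As written, the SAP allows for follow-up time in exploratory efficacy endpoints but not in the AE analysis that serves the main objective.

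**Working it through.** The plan offers no figure to reproduce: Protocol 12.8 makes no formal sample size calculation, and neither document states a dropout rate or a target AE rate. The check asks how far a crude percentage falls below the 96-week risk.

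**Inputs**
- T = 673/365.25 = 1.8426 years (Visit 15, Day 673, Protocol Table 1).
- Dropout by Day 673, d = 15%, 25%, 35%: assumed.
- Event hazard, lambda = 0.01, 0.05 and 0.2 per year: assumed.
- Constant hazards, with exit unrelated to events: assumed.

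**Formulas**
- Exit hazard: mu = -ln(1 - d)/T
- Risk with full follow-up: F = 1 - exp(-lambda T)
- Crude proportion: C = lambda/(lambda + mu) x [1 - exp(-(lambda + mu)T)]
- Person-years to first event or exit, per subject: P = [1 - exp(-(lambda + mu)T)]/(lambda + mu)
- Exposure-adjusted rate: C/P

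**Worked case, lambda = 0.05, d = 25%**
- mu = -ln(0.75)/1.8426 = 0.1561, so lambda + mu = 0.2061
- exp(-0.2061 x 1.8426) = 0.6840
- C = (0.05/0.2061) x 0.3160 = 0.0767
- F = 1 - exp(-0.0921) = 0.0880
- Relative shortfall, from unrounded values: 12.9%
- P = 0.3160/0.2061 = 1.533, so the rate is 0.0767/1.533 = 5.0 per 100 person-years

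**Results**

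| Dropout | Crude at 0.05/year | Full 96-week risk | Shortfall at 0.05/year | Shortfall over 0.01-0.2/year | Rate per 100 person-years at 0.05/year |
|---|---|---|---|---|---|
| 15% | 8.1% | 8.8% | 7.6% | 7.2-7.7% | 5.0 |
| 25% | 7.7% | 8.8% | 12.9% | 12.3-13.1% | 5.0 |
| 35% | 7.2% | 8.8% | 18.5% | 17.7-18.7% | 5.0 |

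**Two groups, same hazard.** Take a true 96-week risk of 10%, with T = 1.84 years and lambda = -ln(0.9)/1.84 = 0.0573. At 10% and 35% dropout the crude percentages are 9.5% and 8.2%. The rate is 5.73 per 100 person-years in both.

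**Timing of exit.** If all exits came at week 4, a 10% risk would show as (1 - d) x 10% + d x [1 - exp(-lambda x 4 weeks)]. That is 9.0%, 8.1%, 7.1% and 6.2% at dropout of 10%, 20%, 30% and 40%.

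**Front-loaded events.** Assume a 30% risk, all within the first 8 weeks: hazard -ln(0.70)/(56/365.25) = 2.326 per year, then zero. At dropout of 15%, 25% and 35% the crude percentage is 29.8%, 29.7% and 29.5%. The rate is 24.6, 26.0 and 27.6 per 100 person-years, because later exits remove event-free time. Here the crude figure is stable and the single rate drifts, so the remedy should not be applied to every AE table.

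**Pooled column.** Assume 40% GI AEs in De Novo subjects (the DMF figure in Protocol 3.3, borrowed as an assumption), 5-10% in rollovers and a 50% rollover share. The overall column would read 0.5 x 40% + 0.5 x 5% = 22.5%, up to 0.5 x 40% + 0.5 x 10% = 25%.

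**The case against.** The strongest reply is that this is an open-label descriptive study with no control arm and no planned between-group test, and that a crude percentage validly describes the proportion of subjects with an event while actually treated. That stands as far as it goes. The shortfall is measured against risk over a full 96 weeks, a target the plan implies through its objective but never defines.

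A reader might infer that long-term safety as a whole rests on crude AE percentages. It does not: SAP 3.6.5 to 3.6.7 add by-visit laboratory, vital-sign and ECG summaries, potentially clinically significant values, shift tables, lymphopenia grade and C-SSRS.

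A reader might also infer that the enrollment groups cannot be compared. That is too strong. Each group has its own column, all have the same planned 96 weeks, and exposure and disposition are reported by group (SAP 3.1.2, 3.4). A descriptive comparison is possible; it becomes unreliable if dropout differs, and prior selection and exposure differ in any case.

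Nor does the overall column hide first-exposure events, since it stands beside the group columns and no section says tolerability will be read from it. The De Novo column is itself not purely first-exposure. Protocol 5.2 provides for subjects already receiving DMF, which shares the active metabolite, and Protocol 7.7.1.2 leaves the timing of stopping DMF before Visit 2 to the Investigator.

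Finally, mock tables and specifications are separate documents (SAP 8 and 9) and could contain rates. The SAP's own list of AE tables does not mention any.

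**Conclusion.** The point holds for AE incidence, and chiefly for events that accrue over time. Under constant hazard and exit unrelated to events, the crude percentage falls short of 96-week risk by about 7-8%, 12-13% and 18-19% (relative) at 15%, 25% and 35% dropout. The dropout figures are assumptions; the shortfall is larger if exits cluster early. It can also create a difference between enrollment groups that reflects follow-up alone, but differential attrition is an inference from the rollover criterion and not something the documents establish.

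Early GI and flushing events, assuming they cluster in the first weeks, are little affected because the event usually precedes exit. For these the practical matter is which column is read. The calculation does not support replacing crude percentages throughout. This is a cheap improvement, not a flaw that invalidates the planned tables.

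**What to change.** - For serious AEs, and for the SAP 3.6.4 categories that accrue over time (such as infections, malignancies, lymphopenia, liver and renal injury), add by enrollment group the number of subjects with a first event per 100 person-years to first event or end of treatment. Use the first- and last-dose dates behind SAP 3.4. State one end date for both events and person-time, because 3.4 stops at the last dose and the treatment period in 3.6.2 at end of treatment.
- For the same events, add incidence by 12-week interval or a time-to-first-event estimate, since a single rate misleads when risk is front-loaded.
- Keep crude percentages for early tolerability events. State that they are read from the enrollment-group columns and not from the overall column, and note that De Novo subjects switching directly from DMF are not first-exposure.

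The cost is a few more tables and modest programming, with no new data collection. Exposure adjustment deals with unequal follow-up only. It does not remove the selection of rollovers as completers of an earlier treatment period, and the report should say so.
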